11. STATISTICAL METHODS

11.1 Analysis Sets

The primary analyses of 90-day mortality will be performed in an Intention-to-Treat (ITT) framework using survival analysis. Specifically,

- (1) we will use all-cause mortality in the first 90-days as the primary outcome event of interest. We will compare the distributions of time to mortality between the two treatment arms. In the primary analysis, mortality event times greater than 90 days will be censored at the 90 days or at the time of liver transplant, whichever comes first. We will use the Logrank test to compare the survival functions of the two treatment groups. Cox regression analysis can be performed if it is necessary to control for the influences of unbalanced patient characteristics, such as MELD score, between the treatment groups. If evidence suggests a violation of the hazard function proportionality, we will conduct an analysis of the restricted mean survival time (RMST) of the first 90 days.
- (2) as a secondary analysis, we will compare transplant-free survival in the first 90 days of treatment initiation as between the two treatment arms, as done in other clinical trials. We will perform logrank test, Cox regression model, and RMST analyses as appropriate.
- (3) we plan to conduct one interim analysis and one final analysis for this trial. The interim analysis will be conducted when **129** patients, half of the enrollment number, complete the 90-day follow-up. We use the group sequential method to control the type 1 error rate of the trial.
- (4) as another secondary analysis, we will examine the treatment effects in patients with baseline MELD scores ≤ 25 and > 25 by assessing the equality of treatment effects of the anakinra in high and low MELD groups, we will test the interaction between the intervention indicator and baseline MELD score in the Cox regression model.

Complete details of the proposed statistical analyses, including a single interim analysis, can be found in the Revised Statistical Analysis Plan (SAP).

11.2 Determination of Sample Size

The primary analysis will be comparisons of 90-day mortality of Anakinra plus zinc vs Prednisone using survival analysis. Mortality event times greater than 90 days will be censored at 90 days or at time of liver transplant, whichever comes first. The experiment-wise significance level will be 5%. The most recent data from the AlcHepNet consortium suggest a 90-day mortality rate for prednisone is approximately 20%. We estimate that with a total of 258 participants (129 per treatment arm), we will be able to detect a clinically significant hazards ratio of 0.325, which translates to a 13% reduction in 90-day mortality, i.e., 80% survival in prednisone vs 93% in anakinra plus zinc groups with 85% power by using two-sided logrank tests. We use O'Brien and Fleming α -spending function to determine the efficacy stopping boundaries for the sequential tests. Specifically, if the test statistics of the log-rank test is greater than 2.963 or less than -2.963, we will claim a significant difference between the two treatments and stop the trial. Otherwise, we will continue enrolling more patients until the full sample size is reached and then the final analysis will be performed. For the final analysis, if the test statistic value is greater than 1.969 or less than -1.969, we will claim a significant difference between the treatments. Otherwise, we will declare that no statistically significant difference is detected.

Besides the group sequential tests, we have in place an early stopping rule for futility based on conditional power. At the time of interim analysis, we will calculate the conditional power, i.e., the probability of claiming difference at the end of the trial given the data at the interim analysis. We will stop the trial for futility when the conditional power is less than 0.1. In other words, based on data that become available at the interim analysis, assuming that the current trend continues, we should early stop the trial if the probability of declaring anakinra + zinc superior in the final analysis is low

(e.g., less than 10%). We use this early stopping rule to limit patient exposure to a potentially ineffectual treatment.

11.3 Safety Analysis

Descriptive statistics will be used to summarize safety data to allow a comparison between groups. Safety data, including AEs, clinical and laboratory observations and physical examination findings, and other safety related outcomes will be summarized by treatment group.

11.3.1 AEs

AEs will be labeled according to standard medical terminology using the case report forms provided. Summary tables of treatment-emergent AEs will be provided. A TEAE is any AE that newly appeared, increased in frequency, or worsened in severity following initiation of study medication. The incidence of TEAEs will be tabulated by system organ class and preferred term for each treatment group, and by severity and relationship to treatment. Tables of TEAEs leading to study medication discontinuation and SAEs will be provided.

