2.2 Rationale for Trial Design and Dose for Study Medication

2.2.1 Study Rationale:

Severe AH continues to be associated with a high mortality and represents a significant public health burden⁸⁻¹³. Prednisone is the standard of care but is associated with a modest and transient survival benefit at best and increased risk of severe bacterial and fungal infections¹⁴⁻¹⁶. A recent large study indicated that pentoxyfylline is not significantly superior to placebo¹⁵. While several new targets are being evaluated, they are not sufficiently powered to provide definitive data. There is therefore a need for well-designed, appropriately powered efficacy (phase 2B or 3) trials to define the utility of newer therapies for severe AH against prednisone.

2.2.2 Rationale for Prednisone in Severe AH, current standard of care for severe Acute Alcoholic Hepatitis (AAH):

Corticosteroid therapy is recommended by the American Association for the Study of Liver Diseases as primary treatment for participants with severe AAH, defined by the Maddrey DF > 32 based on Class I, level A evidence¹. Participants with DF < 32 have six-month survival of $> 85\%$ whereas those with DF > 32 have a survival of only 60%. Almost all trials of corticosteroids have treated participants for 28 days. Although short-term mortality is reduced by 28 days of corticosteroids, 6-month survival is similar to standard care. Many reasons account for late deterioration in steroid treated participants. Infections develop after the first 30 days in some participants treated with steroids. Tapering the dose of steroids (median of 15 days) after 50% improvement in total bilirubin and prothrombin time combined with enteral nutrition reduced the risk of late infections¹⁷. The investigators postulated that the benefit of enteral nutrition was mediated through improvement in integrity of the gut mucosal barrier and reduced gut bacterial translocation and endotoxemia.

Early improvement in bilirubin within the first week is predictive of a good response to corticosteroids at 28 days¹⁸. Although corticosteroids improve survival in a subset of participants with severe AAH, some participants do not respond, either because of steroid “resistance” or due to the underlying severity of the disease. Steroids are not well tolerated in participants with active GI bleeding or systemic infections.

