Corticosteroids represent a clinically tested treatment for severe AH and will be offered to a third of the participants in this randomized clinical trial.

2.2.3 Rationale for testing anakinra plus zinc as novel drugs for severe AH against the standard treatment (Prednisone in Arm 2):

There are currently no new drugs formally approved by the FDA for severe AH. The rationale to repurpose already available agents for AH treatment is to generate evidence to support moving to pivotal trials by the drug manufacturers or support the off-label use of these compounds and thus provide much needed benefit to those with severe AH.

2.2.4 Clinical applications of anakinra:

Preliminary data from the interim analysis of the ongoing clinical trial from the Defeat Alcoholic Steatohepatitis (DASH) UO1 consortium suggests that the treatment arm with anakinra plus pentoxiphylline plus zinc may provide better survival at day 90 and 180 compared to the steroid treated group. Side effects including infection rates were comparable between the anakinra and steroid arms.

Anakinra blocks the effects of IL-1 by inhibiting the binding of IL-1 β and IL-1 α to the IL-1 receptor. It is FDA-approved for treatment of moderate to severe rheumatoid arthritis (RA) since 2001, and is used also in patients with Still's disease, and in familial cold autoinflammatory and Muckle-Wells syndromes²⁰⁻²².

Anakinra has an excellent safety profile compared to other biological therapies. The rate of serious infections was 3.2 per 100 participant-years in participants exposed to Anakinra²³. A meta-analysis of trials evaluating anakinra in RA reported a 1.4% incidence of serious infections with anakinra, compared with 0.5% with placebo, although this difference was not significant after adjustment for underlying comorbidities²⁴. This is important given that participants with severe AH are prone to bacterial infections. No adverse reactions or microbial superinfections were attributable to anakinra treatment in participants with severe sepsis²⁵. Other FDA approved drug candidates for inhibiting IL-1 are canakinumab and rilonacept^{26,27}, that are human monoclonal antibodies and both target IL-1 β (and not IL-1 α). The advantage of anakinra is that it prevents both IL-1 β and IL-1 α effects. An additional advantage of the anakinra is its short half-life for participants with alcoholic liver disease given the concern of susceptibility to infections in this participant population.

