Group 1: Standard of care **plus** prednisone (40 mg orally) once daily on Days 1-30 and matching placebos for Anakinra (1 syringe s.c. once daily on Days 1-14) and zinc (matched pill once daily on Days 1-90).

Group 2: Standard of care **plus** Anakinra (100 mg s.c.) once daily on Days 1-14, zinc sulfate 220 mg once daily on Days 1-90, and placebo for prednisone (matched pill once daily on Days 1-30).

Lille score will be calculated from day 7 labs, participants will stop prednisone or prednisone placebo if Lille score >0.45.

Figure 1. Distribution of study drugs and placebo

Participants or guardian will be instructed in subcutaneous injection technique to continue self-administration of these experimental treatments after discharge from the hospital. Study personnel will ensure participants and guardian are proficient in the technique before the end of study visit.

Relevant clinical care parameters will be recorded on days specified. As noted above, attention will be paid to recording concomitant care provided to treat complications related to AH or portal hypertension including those treatments not specified by protocol, including but not limited to, antibiotics, IV fluids, albumin, pressors, renal replacement, etc.

Standardizing study conduct and good clinical practice (GCP)

Variations in protocol implementation and clinical care can have a major impact on trial outcomes. This will be optimized by: (1) GCP training and certification of all study personnel, (2) investigator/coordinator training and certification prior to site activation, (3) monthly performance reports, (4) development of manual of operations that provide best practices and study procedures to follow, and (5) annual investigator meeting to review developments and clinical and trial practice patterns.

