6.4 Dose, Administration and Blinding

Two treatment groups will be evaluated in the trial: 1) Prednisone, and 2) Anakinra plus zinc

Participants will be instructed to begin dosing on day 1. Oral study medication should be taken with water as instructed on study drug label. Patients will receive two oral medications. Bottle 1 will be Prednisone or Placebo and will be taken daily on Days 1-30 per protocol. Bottle 2 will be Zinc Sulfate or Placebo and will be taken daily on Day 1-90 per protocol.

Participants must be instructed to swallow the capsule whole; they must not open capsule.

Subcutaneous study medication should also begin on Day 1 and be administered daily on Days 1 to 14.

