10. ADVERSE EVENTS

10.1 Definition of Adverse Events & Reporting Period for Adverse Events

Safety will be assessed in terms of AEs. All AEs, whether observed by the investigator, reported by the participant, noted from laboratory findings, or identified by other means, will be recorded from Day 0 until the participant completes trial participation (D-180).

AEs are defined as any untoward medical occurrence associated with the use of the study medication in humans, whether or not considered related to study medication. An AE (also referred to as an adverse experience) can be any unfavorable and unintended sign (e.g., an abnormal laboratory finding), symptom, or disease temporally associated with any use of the study medication, without any judgment about causality and irrespective of route of administration, formulation, or dose, including an overdose. For this trial, study medication refers to Anakinra, zinc, Prednisone, or placebo in the double-blind phase.

AEs include but are not limited to: (1) a worsening or change in nature, severity, or frequency of condition(s) present at the start of the trial; (2) participant deterioration due to primary illness; (3) intercurrent illness; and (4) drug interaction.

Participants should be questioned in a general way, without leading the participant or asking about the occurrence of any specific symptom. The investigator should attempt to establish a diagnosis of the event based on signs, symptoms, and/or other clinical information. The diagnosis and not the individual signs/symptoms should be documented as the AE. For example, if the underlying disease process is a stroke, it would not be appropriate to record the AE by describing the symptoms “sudden numbness, dizziness, and difficulty speaking.” The AE medical term of “stroke or cerebrovascular accident” should be recorded as it more accurately describes the AE. Following questioning and evaluation, all AEs, whether believed by the investigator to be related or unrelated to the study medication, must be documented in the participant’s medical records, in accordance with the investigator’s normal clinical practice and on the AE source Document. Each AE is to be evaluated for duration, intensity, frequency, seriousness, outcome, other actions taken, and relationship to the study medication.

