11.3.2 Clinical Laboratory Evaluations

Descriptive statistics summarizing central laboratory data (hematology, chemistry, and coagulation) will be presented for all trial visits. Changes from pretreatment to each trial visit will also be summarized by treatment group/arm.

- a. The primary analyses of 90-day mortality will be carried out in an ITT framework using the logrank test or Cox regression. Time-to-death will be censored at 90 days or at liver transplant, whichever comes first. In addition to the logrank test, we will perform Cox regression analyses. The models will include baseline MELD score as well as other covariates deemed to be unbalanced or to effect survival. Tests will be performed at a two-sided nominal significance level of 5%. If the proportional hazard assumption is not met, we will compare the restricted mean survival time at 90 days.

Comparisons of binary survival indicators will be performed as alternative analyses, by using either chi-square tests or logistic regression models. In the logistic regression analysis, MELD score as well as other covariates deemed to be unbalanced or to effect survival will be included as covariates.

- b. We will also compare the transplant-free survival functions of the two treatment groups, at 30, 90 and 180 days.
- c. We will also secondarily compare the occurrence of events such as sepsis and renal dysfunction by using survival analysis (logrank test and Cox regression).

Before the groups are compared on these instruments, the baseline data will be examined to look for group imbalance among the survivors. Comparisons will be made using linear regression models that include baseline MELD score and other relevant and/or unbalanced covariates.

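### Adverse event tables run from first dose to Day 180 with no split by onset, so an early infection excess on 14-day anakinra may be diluted

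*Combined protocol and SAP*

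**What the plan says.** Section 11.3.1 opens the window at first dose and never closes it: "A TEAE is any AE that newly appeared, increased in frequency, or worsened in severity following initiation of study medication". Under section 10.1, all adverse events "will be recorded from Day 0 until the participant completes trial participation (D-180"). Section 11.3.1 then tabulates incidence by organ class, preferred term, severity and relationship, with separate tables for serious events and for events leading to discontinuation. None is split by time of onset.

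The exposure windows are much shorter and differ between the drugs. Section 6.4 says of the injections: "Subcutaneous study medication should also begin on Day 1 and be administered daily on Days 1 to 14". For the first oral drug it says: "Bottle 1 will be Prednisone or Placebo and will be taken daily on Days 1-30 per protocol". Zinc or its placebo runs to Day 90.

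The plan also speaks to timing. Section 2.2.2 notes: "Infections develop after the first 30 days in some participants treated with steroids". Section 2.2.4 says, in connection with susceptibility to infection: "An additional advantage of the anakinra is its short half-life". Section 2.3 lists infection as a serious risk of both drugs, above 20% for prednisone and 2-20% for anakinra. Section 4.1 puts infection first among four safety topics.

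The nearest thing to a time-based comparison of infectious events is item (c) of section 11.3.2: "We will also secondarily compare the occurrence of events such as sepsis and renal dysfunction by using survival analysis". It names sepsis but not infection in general, and sets no periods.

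**The concern.** Both arms carry an active drug with an infection risk, so timing is one of the few features that could separate the two. A participant counts once in an incidence row whether the infection began on Day 5 or Day 150. If anakinra raised infection while it was being given, later infections in both arms would shrink the contrast. If prednisone also had a later excess, the two could offset one another.

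The primary objective in the executive summary covers safety as well as efficacy, and infection leads the safety topics. At stake is whether the final report can show when any difference in infection arose, rather than only the total by Day 180.

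**Working it through.** **Plan figures.** The plan attaches no rate, power or precision to the adverse event tables, so there is no figure on this point to reproduce. The sample size is 129 per arm (section 11.2). The 85% power for mortality is not affected.

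**Share of the tabulation window under dosing** (section 6.4 against section 10.1)
- Anakinra: 14/180 = 7.8%
- Prednisone: 30/180 = 16.7% at most
- Zinc: 90/180 = 50%

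**How pooling acts.** Let e be the risk of infection in Days 1-14 and l the risk in Days 15-180 among those without an early infection, ignoring death. Then

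risk by Day 180 = 1 − (1 − e)(1 − l).

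If l is the same in both arms, the pooled risk difference is (e_A − e_P)(1 − l). It keeps its sign and shrinks by the factor 1 − l. The pooled difference is zero only if

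l_P = 1 − (1 − e_A)(1 − l_A)/(1 − e_P).

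**Dilution (all rates assumed).** Take e_P = 10%, e_A = 20% and l = 33% in both arms.
- Prednisone: 1 − 0.90 × 0.67 = 39.7%
- Anakinra: 1 − 0.80 × 0.67 = 46.4%
- Risk difference: 10.0 points in Days 1-14, 6.7 points by Day 180
- Risk ratio: 20/10 = 2.0 in Days 1-14, 46.4/39.7 = 1.17 by Day 180

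Precision with 129 per arm, SE = √[(p_A(1 − p_A) + p_P(1 − p_P))/129]:
- Days 1-14: √[(0.160 + 0.090)/129] = 0.044, so 10.0 ± 8.6 points (1.4 to 18.6)
- Day 180: √[(0.249 + 0.239)/129] = 0.062, so 6.7 ± 12.1 points (−5.4 to 18.8)

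**Range.** With an assumed early 15% versus 5% and equal later risks of 10%, 20% and 30%, the early difference of 10 points becomes 9.0, 8.0 and 7.0. With a smaller assumed early excess, 15% versus 10%, and later risk 33%, it falls from 5 points to 5 × 0.67 = 3.4. The Days 1-14 interval is then 5.0 ± 8.0, so the split table would not be conclusive either.

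**Offset.** This needs a late prednisone excess. With e_A = 20%, e_P = 10% and l_A = 25%, the required l_P is 1 − 0.80 × 0.75/0.90 = 33.3%. With e_A = 15%, e_P = 5%, l_A = 10% and l_P = 20%, the Day 180 figures are 23.5% and 24.0%.

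**The case against.** The strongest case against is that following all events to Day 180 by randomised arm is a legitimate comparison of two strategies, and that other parts of the plan already cover timing.

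- **The assumed rates may point the wrong way.** Section 2.3 gives prednisone the higher infection category. Section 2.2.4 reports comparable infection rates between the anakinra and steroid arms of the earlier trial. This stands as a limit on size: neither source gives rates by period, and neither supports a 10-point early excess.
- **The tables are descriptive.** Section 11.3 plans no test on them, so a loss of power is not the right measure. This stands; the intervals above only illustrate precision.
- **Other safeguards exist.** Relationship to treatment is tabulated, but investigators judge it blinded. Events leading to discontinuation have their own table, but it captures only infections that ended dosing. The DSMB receives unblinded serious event data monthly (section 10.2.3), which protects participants during the trial but does not specify the final comparison. A whole-period logrank test for sepsis can miss effects that change direction. These help in part, and none gives infection by period.
- **Splitting has its own bias.** The design assumes 20% versus 7% mortality by Day 90, so later rows compare differently selected survivors. This stands and belongs beside the tables.
- **The detail may lie elsewhere.** Section 11.1 refers to a Revised SAP for complete details. A window defined there cannot be excluded; section 11.3 contains none.

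**Conclusion.** The point holds as a gap in the safety tables for infection and serious events. As written, section 11.3.1 summarises a 14-day drug over about 180 days with no view by onset, and an early infection excess may be diluted there. On the assumed rates, a doubling of risk in Days 1-14 appears as about 40% versus 46% by Day 180. The size depends wholly on early and late rates that the documents do not give.

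Three stronger readings are tempting and not supported. A reader might infer that an early harm will be cancelled; that needs a late prednisone excess of similar size, and section 2.2.2 says only that some steroid-treated participants develop late infections. A reader might infer that haematological harm is hidden too. However, laboratory values are summarised at every visit (section 11.3.2), blood is drawn on Days 3, 7 and 14 (Table 1), and section 11.3.3 compares arms by mixed models. A reader might also infer that the safety conclusion will be wrong for both drugs; the documents show only that the table could leave the timing unseen.

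Collecting events to Day 180 is sound. What is missing is an additional summary by period.

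**What to change.** Keep the Day 180 table. In section 11.3.1, add tables of treatment-emergent events, serious events and infections by onset period: Days 1-14, 15-30, 31-90 and 91-180. Use as denominator the participants alive and under follow-up at the start of each period. In section 11.3.2(c), name infection alongside sepsis and show cumulative incidence of first infection by arm with death as a competing event. Give period-specific hazard ratios as descriptive support. Fix the periods before unblinding, and check first whether the Revised SAP already sets a window.

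The cost is plan wording and a few tables. Section 10.1 already has each event evaluated for duration, so onset dates should be available. No dose, visit or clinical rule changes. There are three drawbacks:
- Each period has fewer events and wider intervals.
- Later periods compare survivors and are not fully protected by randomisation.
- Day 30 is not a clean exposure boundary, because participants with a Lille score above 0.45 stop prednisone or its placebo at Day 7 (section 5.4.2).
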